2.5 Treatments (study treatment, rescue medication, concomitant therapies, compliance)

2.5.1 Study treatment / compliance

Exposure will be calculated for patients in the Extension safety set from Core baseline. Note that only study ranibizumab as collected in the Drug Administration Record (DAR) eCRF panel will be included. Treatments collected as a concomitant medication will not be included in the study medication analysis. Laser treatment is not a study treatment in the Extension study and therefore will not be collected in the DAR eCRF and will not be summarized here.

Exposure to ranibizumab is defined as the number of injections of ranibizumab received by worst/best eye (as defined in the Core study) and by patient.

The total number of ranibizumab injections will be summarized by worst/best eye and by patient by treatment arm. Summaries will be provided for the entire study period from Core baseline, and for Extension study period. (Note: summary will be summarized by initial treatment received at the baseline of the Core).

The duration of the observation period will be displayed for each treatment arm, and in the Extension study, and overall from Core study baseline.

2.5.2 Prior and concomitant medications

Separate listings and summaries will be produced for ocular and non-ocular, for both prior and concomitant medication, in both Core baseline and Extension baseline based on the Extension safety set.

For Core baseline:

Prior medications are defined as those taken and stopped prior to the date of first study treatment in the Core study. Any medication given at least once on or after the first study treatment date of the Core study will be defined as a concomitant medication. Concomitant therapies taken after the first study treatment in the Core study, which prohibits further use of study treatment

(refers to ranibizumab or study laser in the Core study period and only refers to ranibizumab in the Extension study period) may be summarized separately.

For Extension baseline:

Prior medications are defined as those with an end date prior to the Extension baseline visit. Any medication given at least once on or after the Extension baseline visit will be defined as concomitant medication. Concomitant therapies taken after the extension baseline visit, which prohibits further use of ranibizumab (in the Extension study) may be summarized separately.

Guidance of Data Entry rules in the Extension study eCRF which provides details on handling of Concomitant Medication in Extension study.

- Concomitant Medications continuing at the Core End of Study visit which are ongoing at the time of enrollment into the Extension need to be reported as Extension Concomitant Medication with the same Medication term, Category, Location, Laterality, Is med used for ocular condition, Location of treated condition, Reason and Start date.
- Concomitant Medications continuing at the Core End of Study visit which stopped before enrollment into the Extension, need to be reported again as Extension Concomitant Medication with the same Medication term, Category, Location, Laterality, Is medication used for ocular condition, Location of treated condition, Reason and Start date. Note, that in such a case the Extension Concomitant record must have an end date.
- For subjects where the Core End of Study and Extension baseline visit are occurring on the same date; any ongoing concomitant medication with a start date at this combined Core End of Study and Extension baseline visit, should be recorded in both, the Core and Extension “Prior and Concomitant Medications” CRF pages.
- With regards to vaccinations, if the initial administration was performed in the Core study, this should not be again recorded in the Extension. Only booster doses administered during the Extension study, if any, should be recorded.

Tabular format for Data Entry rules in the Extension study eCRF for Concomitant Medication

Item	Started	Ended	Action for ECRF
Con Meds	Core	Ongoing at beginning of Ext	Record as Con Med in Extension
Con Meds	Core	Gap	Record as Con Med in Extension (=reported as prior medication)
Con Meds	Gap	Gap	Record as Con Med in Extension *(Only if this conmed is of relevance and in the context of a recorded medical history record or (S) AE. Not as a standalone.=reported as prior medication)
Con Meds	Gap	Ongoing beginning of Ext	Record as Con Med in Extension
Con Meds	Ext		Record as Con Med in Extension

Medications will be identified by preferred term (PT) according to the latest World Health Organization (WHO) Drug Reference List dictionary and ATC code. Tables will show the overall number and percentage of patients within the treatment arm receiving at least one dose of the medication ordered by decreasing frequency in the ranibizumab 0.2 mg treatment arm.

For missing medication date, please refer to [Appendix 4](#) for imputation rule.

2.5.3 Surgical and medical procedure

Surgical and medical procedures will be displayed separately for Core and Extension studies, and separate from concomitant medications.

Guidance of Data Entry rules in the Extension study eCRF which provides details on handling of Surgeries and procedures in Extension study:

- It is not expected that records for surgery and procedures in the Core study must be re-entered in the Extension study, as they are usually not continuing over a long period of time. However, if any, records are expected to match (with the exceptions of end dates).
- Procedures which occurred after end of Core study and ended prior to enrollment in to the Extension study should be entered in Extension medical history.

The same approach will be taken to display surgeries and procedures as specified for concomitant medications in [Section 2.5.2](#). Surgical and medical procedures will be identified by primary system organ class and preferred term according to the WHO Drug Reference List dictionary.

2.6 Analysis of the primary objective

2.6.1 Primary endpoint

The primary efficacy variable is the visual acuity (VA) in the better-seeing eye at the patient's fifth birthday as recorded by the investigator.

The primary efficacy analysis will be based on the Extension safety set.

Note that the ranibizumab 0.2 mg arm includes those patients that received ranibizumab 0.2 mg at baseline in the Core study. This includes patients that received laser treatment at a later date in either the Core or Extension study. Patients that permanently discontinue treatment with ranibizumab 0.2 mg are also included in primary efficacy analysis. However, patients for which the value of the primary variable is missing are excluded. A similar approach is taken for the ranibizumab 0.1 mg arm.

Similarly, the laser arm includes those patients that received laser at baseline in the Core study CRFB002H2301. This includes patients that received ranibizumab 0.2 mg treatment at a later date in either the Core or Extension study. Patients that permanently discontinue treatment with laser are also included in the primary efficacy analysis. However, patients for which the value of the primary variable is missing are excluded.

2.6.2 Statistical hypothesis, model, and method of analysis

If the primary hypothesis testing in the Core study shows statistical significance, the primary objective is to compare ranibizumab 0.2 mg versus laser with an informal testing as follows:

$$H_{01}: \mu_{\text{ranibizumab 0.2 mg}} - \mu_{\text{Laser}} = 0 \text{ versus } H_{A1}: \mu_{\text{ranibizumab 0.2 mg}} - \mu_{\text{Laser}} \neq 0$$

where $\mu_{\text{Treatment}}$ arm is the unknown mean VA in the better-seeing eye at the fifth birthday of patients in the relevant treatment arm.

The hypothesis will be tested by using stratified analysis of variance (ANOVA) using the Cochran-Mantel-Haenszel (CMH) test with the observed VA values (letters) as the ordinal response variable and the treatment arm as the factor (with levels ranibizumab 0.2 mg and laser). The effect of ROP zone at the baseline of the Core study is expected to have an effect at 5 years of age. Hence this variable is used as stratification factor in the analysis.

If the primary hypothesis testing in the Core study does not show statistical significance, only descriptive statistics (i.e., point estimate, and the 95% confidence interval) will be provided for the comparison between ranibizumab 0.2 mg and laser.

In addition, an unstratified two-way ANOVA using VA as the response variable and treatment arm and ROP zone as factors will be performed. This is essentially a one-way ANOVA using VA as the response variable and treatment arm as the factor, without ROP zone as the stratification factor. Two-sided 95% confidence intervals, assuming normality, will be produced for the VA within each treatment arm and the difference in VA between a pair of treatment arms will be calculated from least squares means. No p-values will be displayed for this analysis.

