2.2.1.5 Missing baseline data

Missing baseline data (both Core baseline and Extension baseline) will not be imputed. This includes variables which are not allowed to be collected according to local regulations (e.g. race in France).

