2.4.2 Baseline and demographic characteristics

Descriptive statistics (mean, median, standard deviation, minimum and maximum, quartiles 1 and 3) will be presented for the continuous variables. The number and percentage of patients will be presented for categorical variables.

Table 2-3 shows the allocation of baseline parameters into groups and which are displayed as continuous and/or categorical variables.

Table 2-3 Display of baseline parameters:

	Demographic	ROP characteristics and relevant medical history	Continuous	Categorical
Race	x			x

Ethnicity (based on that of mother)	x			x
Sex	x			x
Gestational age at birth (by completed weeks)	x		x	x
Chronological age at Core baseline (by weeks)	x		x	
Chronological age at Extension baseline (by weeks)	x		x	
Post-menstrual age at Core baseline (by weeks)	x		x	
Post-menstrual age at Extension baseline (by weeks)	x		x	
Corrected age at Extension baseline (by weeks)	x		x	
Birth weight (g)		x	x	x
Body length at birth (cm)		x	x	x
Head circumference at birth (cm)		x	x	x
Lower leg length		x	x	x
ROP zone by patient		x		x
ROP zone by eye		x		x
AP-ROP status by patient		x		x
AP-ROP status by eye		x		x
ROP disease status by patient		x		x
ROP disease status by eye (worst/best)		x		x
APGAR sCore at 1 minute		x	x	
APGAR sCore at 5 minutes		x	x	
Intubation requirement before enrollment (y/n)		x		x
Multiple pregnancy (y/n)		x		x
Number in multiple infants born of a multiple pregnancy		x	x	
Born in study hospital (y/n)		x		x
Time from first diagnosis of ROP to screening visit (weeks)		x	x	x
Time from ROP fulfilling treatment criteria to screening visit (weeks)		x	x	x

Chronological age and Post-menstrual age will be calculated from Core study baseline as below:

Chronological age at Core/Extension baseline (weeks) = [Core/Extension baseline visit date - (start date of the mother's last normal menstrual period + gestational age at birth*7)+1]/7

Post menstrual age at baseline (weeks) = (Core/Extension baseline visit date - start date of the mother's last normal menstrual period+1)/7

Corrected age at Extension baseline (weeks) = [Extension baseline visit date - (start date of the mother's last normal menstrual period + 40*7)+1]/7

The time from a pre-screening event (e.g. diagnosis of a condition or taking a medication) in days will be derived using the formula:

Time since <event> [days] = date of screening– date of event

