4.3 Statistical models and SAS codes

CMH test:

The primary efficacy variable is the visual acuity (VA) in the better-seeing eye at the patient's fifth birthday as recorded by the investigator.

The following primary hypothesis will be used to test the comparison of ranibizumab 0.2 mg versus laser as follows:

$$H_{01}: \mu_{\text{ranibizumab 0.2 mg}} - \mu_{\text{Laser}} = 0 \text{ versus } H_{A1}: \mu_{\text{ranibizumab 0.2 mg}} - \mu_{\text{Laser}} \neq 0$$

where $\mu_{\text{Treatment}}$ arm is the unknown mean VA in the better-seeing eye at the fifth birthday of patients in the relevant treatment arm.

The hypothesis will be tested by using stratified analysis of variance (ANOVA) using the Cochran-Mantel-Haenszel (CMH) test with the observed VA values as the response variable and the treatment arm as the factor (with levels 0.2 mg and laser). Stratification will be based on the ROP zone at the Core study baseline.

The test statistics can be written in the form (Lehmann, E. L. (1975) and Van Elteren, P.H. (1960)):

$$W^* = \frac{\sum_{j=1}^J a_j \sqrt{\frac{n_{0j}n_{1j}}{n_{0j} + n_{1j}}} \left(\frac{1}{n_{0j}} \sum_{k=1}^{n_{0j}} R_{0jk} - \frac{1}{n_{1j}} \sum_{k=1}^{n_{1j}} R_{1jk} \right)}{\sqrt{\sum_{j=1}^J a_j^2 \frac{1}{n_{0j} + n_{1j} - 1} \sum_{i=0}^1 \sum_{k=1}^{n_{ij}} (R_{ijk} - \bar{R}_{\bullet,j})^2}}$$

where R_{ijk} is the VA sCore of subject k within strata j of treatment i , $i=0,1$ denotes the treatment arm, $j=1, 2$ denotes the ROP zone, $k=1, \dots, n_{ij}$ denotes the subjects within the i^{th} treatment arm in the j^{th} ROP zone and $\bar{R}_{\bullet,j}$ is the average VA sCore of all subjects in Zone j .

For large sample sizes (within each strata) the test statistic has a standard normal distribution; therefore the two-sided test would reject the null hypothesis if $|W^*| > Z_{\alpha/2}$, where Z is the $N(0, 1)$ distribution.

The option CMH with SCORESSCORES=TABLE in the OUTPUT statement requests the CMH row means sCore statistics and the corresponding two-sided p-value:

```
proc freq data = <input_dataset sorted> noprint;
tables <stratavar> * <treatmentvar> * <responsevar> / CMH
SCORESSCORES=TABLE ;
output out = <output_dataset> (keep = _CMHRMS_ P_CMHRMS) CMH;
run;
```

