The two-sided p-value will then be converted to a one-sided p-value: For each comparison, if the direction of the observed difference supports the superiority outcome (e.g. mean difference > 0), the two-sided p-value will be converted to a one-sided p-value by dividing by two. If mean difference < 0 , the one-sided p-value will be calculated as 1 - (the two-sided p-value divided by two).

ANOVA model:

The ANOVA analysis will be performed using SAS procedure PROC MIXED.

Stratified ANOVA:

```
proc mixed data = <input_dataset sorted> noprint;
class <treatmentvar> <stratavar>;
model <responsevar> = <stratavar> <treatmentvar> ;
lsmeans <treatmentvar> / om;
estimate ""<treatmentvar>;
run;
```

Unstratified ANOVA:

```
proc mixed data = <input_dataset sorted> noprint;
class <treatmentvar>;
model <responsevar> = <treatmentvar> ;
lsmeans <treatmentvar> / om;
estimate ""<treatmentvar>;
run;
```

Calculating 95% confidence intervals for proportions using Clopper-Pearson method:

[figure not shown]
The confidence intervals for the proportions will be calculated using the Clopper-Pearson method. It will be performed using SAS procedure PROC FREQ with the BINOMIAL option in the TABLES and EXACT statements:

[figure not shown]
```
proc freq data = <input_dataset sorted> noprint;  
by <treatmentvar>;  
tables <responsevar> / binomial (cl=exact );  
exact binomial;  
run;
```

[figure not shown]

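### The visual acuity ANOVA adjusts for ROP zone at most, and section 2.6.2 leaves even that unclear; continuous gestational age should be added beside the zone-only estimate

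*SAP*

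**What the plan says.** Section 2.6.2 tests VA in the better-seeing eye with a CMH test stratified by ROP zone and gives its reason: "The effect of ROP zone at the baseline of the Core study is expected to have an effect at 5 years of age". It continues: "Hence this variable is used as stratification factor in the analysis". Section 4.3 agrees: "Stratification will be based on the ROP zone at the Core study baseline". Section 2.8.1 reuses the same zone-stratified approach for the other arm comparisons and for the worse-seeing eye.

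The confidence intervals come from a separate ANOVA, for which no p-values are shown. Section 2.6.2 labels this model unstratified, then two-way with arm and zone as factors, and then in effect one-way with arm alone. Section 4.3 has code for two models. The stratified one is "model <responsevar> = <stratavar> <treatmentvar>", which holds stratum and arm. The unstratified one is "model <responsevar> = <treatmentvar>", which holds arm only. None of the supportive analyses in section 2.6.4 adds a covariate.

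Table 2-3 in section 2.4.2 lists gestational age at birth and birth weight as continuous and categorical baseline parameters. They are summarised by arm and used in no VA model. On completeness, section 2.2.1.5 says: "Missing baseline data (both Core baseline and Extension baseline) will not be imputed".

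**The concern.** The reason the SAP gives for using zone, an expected effect on the outcome at age five, applies just as naturally to gestational age. That variable measures the degree of prematurity in a trial of retinopathy of prematurity.

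Two things are at stake:

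- **Precision.** The extension has no power-based sample size (section 3) and disclaims Type I error control (section 2.1). If the Core study's primary test was not significant, the arm comparison is only a point estimate with its interval. The width and centring of that interval are then the main result.
- **Balance.** The analysed children entered the Extension (section 2.3), are grouped by treatment received, and have a non-missing fifth-birthday VA (sections 2.6.1 and 2.6.3). Randomisation no longer guarantees balance in such a subset, and nothing in the VA models would correct a measured difference in prematurity.

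The unclear ANOVA description adds to both. If the one-way reading is followed, the reported differences and intervals lack even the zone adjustment that the SAP itself justifies.

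**Working it through.** **Inputs.** The SAP states no sample size, SD of VA, effect size, dropout rate or variance explained by gestational age, so there is no figure to reproduce. Everything below rests on assumptions:

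- R²: share of within-zone VA variance explained by the prematurity covariate, taken as 0 to 0.15.
- d: systematic difference between arms in that covariate, in SD, taken as 0.2.
- 30, 50 or 70 children per arm where a sample size is needed.

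**Formulas.** Proportional fall in the standard error (SE): 1 − √(1 − R²). Equivalent gain in patients: 1/(1 − R²) − 1. Bias left by a zone-only analysis, in SD of VA: √R² × d.

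| R² | Fall in SE | Equivalent extra patients | Zone-only bias at d = 0.2 |
|---|---|---|---|
| 0 | 0 | 0 | 0 |
| 0.05 | 1 − √0.95 = 2.5% | 1/0.95 − 1 = 5.3% | 0.224 × 0.2 = 0.045 SD |
| 0.10 | 1 − √0.90 = 5.1% | 1/0.90 − 1 = 11.1% | 0.316 × 0.2 = 0.063 SD |
| 0.15 | 1 − √0.85 = 7.8% | 1/0.85 − 1 = 17.6% | 0.387 × 0.2 = 0.077 SD |

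**Cost when the covariate is useless.** The formulas ignore the cost of estimating extra coefficients. A simulation (1,500 runs per setting) compared zone alone with zone plus two prematurity covariates correlated at an assumed 0.6. At R² = 0 the mean SE rose from 0.201 to 0.203 with 50 per arm (1.0%), and from 0.259 to 0.265 in one of the two settings with 30 per arm (2.3%). That is a cost of about 1 to 2%; a single covariate should cost less.

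**Net gain in the same simulation, no imbalance.** At R² = 0.10 and 50 per arm the SE fell from 0.200 to 0.192, or 4.0%, slightly below the 5.1% of the formula.

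**Bias in the same simulation, d = 0.2.** At R² = 0.05 and 0.10 the zone-only estimate was off by 0.041 to 0.064 SD, and the adjusted one by at most 0.004 SD. The simulated covariate effect was linear and correctly modelled, which favours adjustment.

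**Scale.** At 50 per arm the SE of the difference is about √(2/50) = 0.20 SD. A bias of 0.045 to 0.077 SD is then 0.045/0.20 = 0.22 to 0.077/0.20 = 0.39 of one SE.

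**The case against.** The strongest reply is that adjusting for one named prognostic factor, with a reason given, is a legitimate choice. The comparison is declared informal and is to be read with caution, and an SE change of a few per cent will rarely alter its reading. This largely stands: the point is an improvement, not an arithmetic error. It does not cover the two descriptions of the ANOVA, which do conflict.

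A reader might infer more than the SAP supports:

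- **That gestational age and birth weight are recorded for every child.** Table 2-3 only lists them, and section 2.2.1.5 foresees missing baseline values. Gestational age is probably close to complete, since the visit windows in section 2.2.1.2 and the age formula in section 2.4.2 need it, but the SAP does not say so.
- **That precision is certainly being lost.** Nothing in the SAP says that either variable predicts VA within zone. If neither does, adjustment gains nothing and costs slightly.
- **That the arms are imbalanced, or that adjustment would remove any resulting shift.** No imbalance is shown. Chance imbalance is already reflected in the SE, and only systematic selection is bias. A linear term removes only the measured, correctly modelled part. The SAP's own 0-letter category and its analysis excluding zero scores show that a floor is expected, so linearity is not assured. VA missing for unmeasured reasons stays unrepaired.
- **That the change is free.** The study is open-label, and section 2.15 presents gestational age descriptively at Interim Analysis II, so a covariate added afterwards follows sight of its distribution.

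**Conclusion.** The point holds as a modest, low-cost improvement together with one needed clarification. VA is adjusted for ROP zone at most, and the text does not settle whether the ANOVA behind the confidence intervals includes zone. Gestational age, a planned continuous variable, is unused in a complete-case roll-over subset grouped by treatment received.

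The size is conditional. For an assumed R² of 0 to 0.15 the effect on the SE lies between an increase of 1 to 2% and a fall of 7.8%. If selective roll-over or dropout left a systematic 0.2 SD difference between arms, R² of 0.05 to 0.15 would leave 0.045 to 0.077 SD of bias in a zone-only estimate. The SAP neither confirms nor excludes these inputs. The CMH test is not at fault.

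**What to change.** In sections 2.6.2 and 4.3:

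1. Remove the conflict by stating which factors each ANOVA contains.
2. Specify an ANOVA of VA on treatment, ROP zone at Core baseline and continuous gestational age at birth, for the better- and the worse-seeing eye. Report its arm differences and 95% confidence intervals beside the zone-only estimates.
3. Leave the zone-stratified CMH test unchanged.
4. Add one line on how a missing gestational age is handled.
5. Label the covariate as added after gestational age was displayed at Interim Analysis II.

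One prematurity covariate is enough; birth weight need not be added. The cost is one term in existing code and a few sentences. The remaining drawback is that the CMH p-value and the adjusted interval come from different adjustments. Keeping the zone-only estimate alongside lets the reader see any difference.

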2.8.1 Secondary endpoints

Continuous variables:

The following objectives will be assessed for the continuous variables below by using the same CMH test approach as the primary analysis with ROP zone at Core baseline as stratification factor.

- The comparison between ranibizumab 0.1 mg and laser with regard to the VA of the better- seeing eye at the patient's fifth birthday
- The comparison of ranibizumab 0.2 mg versus ranibizumab 0.1 mg with regard to the VA of the better-seeing eye at the patient's fifth birthday
- The three pairwise comparisons of treatment arms will be repeated with regard to the VA of the worse-seeing eye at the patient's fifth birthday

Again, one needs to be cautious interpreting the p-values when they show statistical significance and the point estimates indicate ranibizumab treatment is better than laser.

Recurrence of ROP is defined as ROP receiving any study intervention after the first study treatment of the Core study.

Binary variables:

- The absence of all ocular structural abnormalities (see below for the definitions) at or before the patient's 2 years' corrected age and fifth birthday.
- The absence of active ROP at 52 weeks post Core baseline

The CMH test with ROP Zone as assessed at the baseline of the Core study as stratification factor will be used for inference concerning binary secondary efficacy variables. Mantel-Haenszel odds ratios and their two-sided 95% confidence intervals will be presented. The rejection of the null hypothesis (equality of proportions) and the Mantel-Haenszel odds ratio being in favor of the hypothesized superior treatment should be interpreted with caution.

The absence of active ROP in both eyes is defined by the absence of all of the following features:

- Vessel dilatation of plus disease in at least 2 quadrants (some persisting tortuosity is allowed)

- Extra-retinal vessels extending from the retina into the vitreous and judged to be a sign of active ROP disease.

The absence is defined as the absence of both of the above individual components at a particular time point, e.g., at week 40.

The absence of all ocular structural abnormalities is defined by the absence of all of the following fundus features in both eyes at or before a particular time point, e.g., week 40 after the first study treatment in the Core study:

- Substantial temporal retinal vessel dragging causing abnormal structural features/
macular ectopia
- Retrolental membrane obscuring the view of the posterior pole

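### SAP 2.6.2 describes the ANOVA behind the visual-acuity estimates both with and without ROP zone, and 4.3 does not say which model is reported

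*SAP*

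**What the plan says.** SAP 2.6.2 has two branches for the primary comparison of ranibizumab 0.2 mg with laser.

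- **Core test significant:** "The hypothesis will be tested by using stratified analysis of variance (ANOVA) using the Cochran-Mantel-Haenszel (CMH) test", stratified by ROP zone. The reason given is that "The effect of ROP zone at the baseline of the Core study is expected to have an effect at 5 years of age".
- **Core test not significant:** "only descriptive statistics (i.e., point estimate, and the 95% confidence interval) will be provided". No model is named in that sentence.

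A further paragraph, opening with 'In addition' and not conditional on the Core result, says that "an unstratified two-way ANOVA using VA as the response variable and treatment arm and ROP zone as factors will be performed". The sentence after it describes the same analysis: "This is essentially a one-way ANOVA using VA as the response variable and treatment arm as the factor", "without ROP zone as the stratification factor". The within-arm 95% intervals are attached to this analysis, and "the difference in VA between a pair of treatment arms will be calculated from least squares means". No p-values are shown for it.

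Section 4.3 prints two PROC MIXED programs. The one labelled 'Stratified ANOVA' has zone and treatment in the model. The one labelled 'Unstratified ANOVA' has treatment only. The CMH program in the same section keeps only the row-mean-score statistic and its p-value.

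For the other visual-acuity comparisons, including the worse-seeing eye, 2.8.1 proceeds "by using the same CMH test approach as the primary analysis with ROP zone at Core baseline as stratification factor". It says nothing about the estimate.

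**The concern.** A model with zone as a factor is not a one-way model, so the two sentences cannot both describe the analysis. The paragraph matters because it is the only place in 2.6.2 that says where arm intervals and pairwise differences come from. The CMH test supplies neither.

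Section 2.1 disclaims formal inference, so the estimate and its interval carry the comparison. In the descriptive-only branch they are all of it. If the choice between the two models is left open, it can be made after the data are seen. If the one-way model is used, the estimate ignores the factor that the SAP gives as its reason for stratifying, and it stands beside a test that accounts for that factor.

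**Working it through.** **1. The text against the code**

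| Source | Label used | Terms in the model |
|---|---|---|
| 2.6.2, first ANOVA sentence | unstratified, two-way | treatment, zone |
| 2.6.2, next sentence | one-way | treatment |
| 4.3, first program | Stratified ANOVA | zone, treatment |
| 4.3, second program | Unstratified ANOVA | treatment |
| 2.6.2, hypothesis test | stratified ANOVA, by CMH | zone as stratum; test only |

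The label in the first ANOVA sentence points to the second program, and its list of factors points to the first. No sentence assigns either program to an output. Nor does the printed code settle it: LSMEANS carries no CL or DIFF option, and the ESTIMATE statement has a blank label and no coefficients.

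**2. How far apart the two readings could be**

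The SAP gives no zone effect, zone split, SD or arm size, so there is no figure of its own to reproduce. Assumed here: within-zone SD 20 letters, Zone I share 0.35, 55 children per arm, zone effect *d* of 5, 10 or 15 letters.

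*Width.* Between-zone variance = *d*² × 0.35 × 0.65. Its share of total variance is R² = that / (400 + that). Ratio of unadjusted to adjusted width = 1/√(1 − R²).

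| *d* | Between-zone variance | R² | Width ratio |
|---|---|---|---|
| 5 | 5.69 | 1.4% | 1.007 |
| 10 | 22.75 | 5.4% | 1.028 |
| 15 | 51.19 | 11.3% | 1.062 |

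*Shift of the estimate.* This is the zone effect times the difference in Zone I share between the two arms: 5 × 0.05 = 0.25 letters; 10 × 0.10 = 1.0; 15 × 0.15 = 2.25. It is zero when the arms are balanced on zone.

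*Scale.* 95% half-width with zone in the model: 1.96 × 20 × √(2/55) = 7.48 letters, ignoring the small loss from imbalance.

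*Check by simulation* (20,000 datasets per setting, 55 per arm). With 19 Zone I children in every arm, the mean width ratios were 1.007, 1.029 and 1.064, with no shift. With 22 against 16 Zone I children in the compared arms and a 10-letter effect, the mean shift was 1.09 letters in size, which is 10 × 6/55.

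*Other assumptions.* With 60 per arm, 40% in Zone I and a 20-letter zone effect, the half-width goes from 7.16 to 7.97 letters (about 11% wider). A 10-point imbalance then shifts the estimate by 20 × 0.10 = 2.0 letters.

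**3. Two arms or three in the fit**

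In the simulations, the zone-plus-treatment difference fitted to the two compared arms equalled the difference weighted as in the CMH test. With Zone I counts of 22, 16 and 19, a three-arm fit departed from it by about 0.5 letter at the 95th percentile. In return, two-arm fits let one arm's adjusted mean vary between its pairs, here by 10 × (41/110 − 38/110) = 0.27 letter.

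**The case against.** **Both models were probably meant.** The Amendment 5 entry in the change log records that reference code for the unstratified ANOVA was added, which suggests a one-way model placed beside an existing zone model and a badly merged text. This is plausible. A reader might infer that the zone-plus-treatment code is orphaned and that the only estimate in 2.6.2 leaves zone out. The documents do not support that, because it requires the word 'unstratified' to override the factors actually listed. Even so, if both models are run, the SAP still does not say which one is reported.

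**The descriptive branch does have a source.** The ANOVA paragraph is unconditional and yields intervals and differences without p-values, which is what that branch promises. A reader might infer that the SAP gives no way to obtain the descriptive estimate. That goes too far. What remains is that 'In addition' does not tie the paragraph to the branch, and its wording does not explicitly attach an interval to the difference. The change log also refers to the protocol for the descriptive primary analysis, and the protocol is not at hand.

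**The effect is small and nothing is inferential.** This stands. The 2.25-letter shift pairs the largest zone effect considered with a 15-point imbalance. Under simple randomisation the standard error of the imbalance is √(2 × 0.35 × 0.65/55) = 0.091, so a gap that large in either direction has a chance of about 10%.

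**Separate two-arm fits are a preference.** This also stands. Nothing in 2.6.2 or 4.3 restricts the ANOVA to two arms.

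**Conclusion.** The contradiction is in the text and leaves the reported visual-acuity estimate undefined. It carries over to the descriptive-only branch if, as is likely, the ANOVA feeds that branch. For the worse-seeing eye, 2.8.1 names only the test.

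On assumed inputs the two readings differ modestly: intervals about 1% to 6% wider without zone, for zone effects of 5 to 15 letters, and a shift of 0 to about 2 letters against a half-width of about 7.5. These sizes depend on a zone effect, zone split, SD and arm size that the SAP does not give.

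A reader might infer a threat to type I error. Section 2.1 rules that out, since no significance claim is planned. The harm is to the clarity and consistency of a descriptive estimate. The point should be corrected, but it does not undermine the study.

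**What to change.** In 2.6.2, state that arm means, pairwise differences and their 95% intervals come from the zone-plus-treatment model (the 'Stratified ANOVA' code in 4.3), in both branches. Say in 2.8.1 that the same holds for the remaining pairwise comparisons and for the worse-seeing eye. Delete the two conflicting descriptions, keep the one-way model as a labelled sensitivity analysis, and use the same labels in 2.6.2 and 4.3.

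Complete the 4.3 code so that it requests the intervals and differences, for example with CL and DIFF on LSMEANS, or with a labelled ESTIMATE statement that has coefficients. State whether the model is fitted to the two compared arms or to all three. Either is workable. The two-arm fit has the CMH weighting, and the three-arm fit gives one adjusted mean per arm.

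The cost is SAP wording plus a small code edit. No new data are needed.
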